5. PLANNED ANALYSES

5.1. Interim Analyses

Data summaries will be provided to the Data Monitoring Committee (DMC) as specified in the DMC Charter. Interim analyses of PK, safety and effectiveness data may be conducted after at least 15 subjects complete 48 weeks of treatment (through Part 2) using interim locked data as defined in the protocol to support the New Drug Application (NDA) submission. An additional interim analysis may be done when all subjects complete end of Part 2/48 weeks of treatment. Effectiveness data are not collected after the Week 48 visit. Safety and dosing tables for the end of 48-week analysis will only include data through the Week 48 visit; for all other analyses, all available data will be reported unless otherwise specified. Additional analyses may be conducted to support regulatory filings, safety updates, and publications.

5.2. Final Analysis

The final analysis of disposition, dosing, and safety data collected in Parts 1, 2, and 3 will be conducted once the last subject completes or discontinues his or her respective parts, the resulting clinical database has been cleaned and quality checked, the analysis populations have been finalized, and database lock has occurred. Disposition, dosing, and safety data will be summarized through the end of study (Week 144).

6. GENERAL CONSIDERATIONS FOR DATA ANALYSES AND HANDLING

This section addresses the definitions, algorithms, imputations, and conventions that will apply to the analysis and handling of the data in general. Rules that are data specific will be addressed in the detailed discussions of individual summary tables.

6.1. General Summary Table and Individual Subject Data Listing Considerations

Summary tables and listings will include “footers” providing:

1. Date of output generation.
2. SAS program name that generates the output.
3. File path(s) to datasets used in the SAS program, including names of datasets.
4. Any abbreviations used in the body of the table.
5. Any other output-specific details that require elaboration.

Version 9.4 or higher of the SAS system will be used to analyze the data and to generate tables, figures, and listings. All SAS programs prepared to analyze the data will be properly annotated to permit uninvolved outside statistical experts to replicate all the analyses specified in this statistical analysis plan (SAP).

The date of output generation links the output to the locked and archived database to allow replication of the results.

6.2. General Post Text Summary Table and Individual Subject Data Listing Format Considerations

Tables and listings will be numbered to reflect main levels of unique tables and listings and sub-levels of replicate tables and listings with up to 2 digits per level (eg, Table XX.Y.Z.).

The first level number should be consistent with the corresponding clinical study report (CSR) appendix in which the tables, figures or listings will appear. Following the International Conference on Harmonisation of Technical Requirements for Registration of Pharmaceuticals for Human Use guideline E3 (ICH-E3), all post text tables and figures should have first level 14 and data listings should have 16.2.

Subject accounting and final disposition, baseline, and demographic profile will appear as the first sub-level (Table 14.1 series). Analysis of berotralstat concentration and non-compartmental PK analysis will be included in Section 14.2, however, analysis results of population PK modeling will be provided in a separate pharmacometric report. Effectiveness data will also be included in Section 14.2. Safety data will be included in Section 14.3. Analysis of palatability

data will be in Section 14.4. For subject data listings, 16.2.1.x and 16.2.2.x includes subject accounting, 16.2.3.x includes analysis populations and enrollment by country and site, 16.2.4.x includes demographics and medical/medication histories, 16.2.5.x includes dosing, drug accountability and compliance, and PK concentration, 16.2.6.x includes effectiveness, 16.2.7.x includes adverse events, 16.2.8 includes laboratory results, and 16.2.9.x includes palatability.

The title of the output should be complete, accurate, and concise. If convenient, the parameter and unit of measurement can appear in parentheses to conserve space in the body of the table. For example, the summary of vital signs title could read “Summary of Sitting and Standing Blood Pressure (mmHg) and Heart Rate (bpm).” Whether in the title or body of a table or listing, units must always be specified for all appropriate data. The last line of the title should provide the analysis group being summarized (eg, Safety Population or PK Population).

If possible, variables being summarized, and statistics reported should appear in the leftmost column of a table. The next columns for treatment groups should report the data from left to right for all treated subjects with the investigational drug, by cohort. Any row with all zeros will not appear except with reasons for not completing the study. Summary tables clearly indicate the number of subjects to which the data apply, and unknown or not performed are distinguished from missing data. PK tables are addressed in Section 10.

In general, the listings should be sorted and presented by cohort, subject number, and study day or time of assessment. From left to right, the cohort number, subject number, visit number, and visit date / relative day should appear.

All tables and listings must have explanatory notes that give the definition of all derived variables and decodes for coded data. Due to space limitations, tables and listings may require a page of notes as a one-time preface to the output.

6.3. Data Management

A data management plan will be developed and approved prior to commencement of data entry.

Data will be captured using the Medidata electronic data capture system. Electronic validation steps (edit checks) will be utilized, and data cleaning will occur in conjunction with each site. Prior to transfer of data provided by vendors (eg, laboratory data), a data transfer agreement including specifications for the type of file, definitions of variables, and contact information for the sending and receiving parties will be developed and finalized. The standard operating procedures (SOPs) of PharPoint, the selected data management, statistics, and programming vendor for this study, will be used.

Data will be mapped to Study Data Tabulation Model (SDTM)-compliant datasets prior to creation of Analysis Data Model (ADaM)-compliant derived datasets for use in the creation of summary tables. All analyses will be generated using SAS[®] v9.4 or above and in accordance with PharPoint SOPs.

6.4. Data Presentation Conventions

Continuous data will be summarized using the number of subjects with available data, mean, standard deviation (SD) or standard error of the mean (SEM), median, minimum, and maximum. Categorical data will be summarized using counts/frequencies and percentages. Percentages will be calculated using the total number of subjects per cohort unless otherwise specified.

Means and medians will be formatted to 1 more decimal place than the measured value, SDs and SEMs to 2 more decimal places, and minimum and maximum values to the same number of decimal places. For categorical variables, the number and percentage of responses will be presented in the form XX (XX.X%) where the percentage is in the parentheses, except that 100% will be presented to 3 digits with no decimal. Adverse event data will be presented in the form XX (XX.X%) [XXX] where the number of subjects with at least 1 event (incidence) is the first number and the number of occurrences of an event is in “[]”. Dates will be formatted as DDMMYYYY and times will be formatted in 24-hour time as HH:MM. Partial dates will be handled as described in Section 8.5.

Berotrastat concentration data will be listed and summarized as part of the statistical analysis for this study and included in the Clinical Study Report. Noncompartmental PK parameters will be calculated as described in Section 10.1.2 and included in the Clinical Study Report. PK parameters from population PK modeling will be calculated and summarized as described in the Population PK Analysis Plan and included in the Population PK report.

Wherever possible, data will be decimal aligned.

A table of contents at the end of this SAP provides the expected titles and numbers of the tables, listings, and figures of the final report. Changes to titles or numbering in the final report will not necessitate a revision to the SAP, nor will they be considered deviations from planned analyses. Additional data listings supporting the tables will not be considered a deviation from planned analyses.

6.5. Analysis Populations

6.5.1. Screen Failures

Subjects for whom informed written consent is provided by their P/C and assent is provided (where appropriate), but are not allocated to study treatment, and are noted as screen failures in electronic case report form (eCRF) are considered screen failures. This includes subjects who withdraw consent during the SOC period of the study. Subjects who are “preliminary enrollees” awaiting final confirmation of eligibility will also be considered screen failures if found to be ineligible for study participation. These subjects will not be treated with study drug and will not be summarized other than on the disposition table. Data collected from screen failures may be presented on corresponding data listings.

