^a Subjects will be enrolled at the screening visit. If, after the screening visit, laboratory results are returned that indicate the subject no longer meets the inclusion and exclusion criteria, the subject will be considered a screen failure.

^b Indicates visits where a single, random, plasma sample is collected for PK.

Pediatric patients who are considered good candidates for the study will report to the site for a screening visit. After P/C have provided informed consent, and, where appropriate, children have provided assent, screening assessments may be initiated. Screening assessments will be conducted at the screening visit

although, if necessary, the assessments may take place over a screening period not to exceed 14 days without prior consent of the sponsor. Subjects will be considered enrolled into the study as of the date of the screening visit if all available results satisfy the inclusion and exclusion criteria as of that date. If, after the screening visit, screening results are returned that indicate the subject no longer meets the inclusion and exclusion criteria, the subject will be considered a screen failure. The investigator will provide the P/C with study materials (eg, subject's diary) at the end of the screening visit and request the P/C to record diary data starting at the date of the screening visit and for the next 12 weeks (ie, the SOC treatment period).

To monitor effectiveness, the P/C must begin recording HAE attacks in the subject's diary at the time of subject enrollment, and continue recording through Week 48 (ie, end of Part 2).

SOC Treatment Period: Subjects will continue taking their SOC therapy for HAE (either short-term or long-term prophylaxis, or acute treatment for HAE attacks) for 12 weeks from the screening visit. No additional in-person visits are required during the SOC treatment period; however, at approximately 4 and 8 weeks following screening, site personnel will contact the P/C to assess AEs and the overall status of the subject.

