12.2.1.1. Intent to Treat Population

The intent to treat (ITT) population will include all subjects who satisfy all entry criteria and who enroll into the study. As this study focuses on safety and PK of berotralstat, analyses of the ITT population will likely be limited.

Note that subjects for whom their P/C provided written informed consent but who are not enrolled in the study will be considered screen failures. Subjects who are “preliminary enrollees” awaiting final confirmation of eligibility will also be considered screen failures if found to be ineligible for study participation.

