X	X	X	14.3.5.3.2.3	Distribution Plots for PR Interval Observed Changes Relative to Baseline – All Observations	Safety
X	X	X	14.3.5.3.3.1	Plot of Mean (SD) QRS Observed Changes Relative to Baseline Over Time	Safety
X	X	X	14.3.5.3.3.2	Distribution plots for QRS Changes Relative to Baseline Over Time	Safety
X	X	X	14.3.5.3.3.3	Distribution plots for QRS Changes Relative to Baseline – All Observations	Safety
X			14.4.1.1	Acceptability/Palatability of the Berostralstat Oral Granules (limited to Cohort 2, 3, 4)	Safety

Listings:

NDA IA	End of Part 2 (Wk 48) IA	Final (Safety)	Listing Number	Title	Population
X	X	X	16.2.1.1	Informed Consent	All Subjects
X			16.2.1.2	Screen Failures	Screen Failures
X			16.2.2.1	Inclusion Criteria Not Met/Exclusion Criteria Met	ITT
X	X	X	16.2.2.2	Protocol Deviations	ITT
X	X	X	16.2.2.3	End of Study	ITT
X	X	X	16.2.3.1	Analysis Populations	ITT
X			16.2.3.2	Enrollment by Country and Site	ITT
X	X		16.2.4.1	Demographic and Baseline Characteristics	ITT
X			16.2.4.2	Confirmation of Clinical Diagnosis of HAE	All Subjects
X			16.2.4.3.1	Medical History	ITT
X			16.2.4.3.2	HAE Medical History – HAE Baseline Characteristics	ITT
X	X	X	16.2.4.3.3	HAE Medication History – Past and Current On-Demand HAE Treatment	ITT
X			16.2.4.3.4	HAE Medication History – Past Prophylactic HAE Treatment	ITT
X			16.2.4.4.1	Medications Taken within 30 Days of Screening and Discontinued Prior to Study Drug Initiation	ITT
X	X	X	16.2.4.4.2	Concomitant Medications	ITT
X	X	X	16.2.4.4.3	Use of Concomitant Medications for HAE	ITT
X	X	X	16.2.5.1	Drug Accountability and Compliance	ITT
X	X	X	16.2.5.2	Subjects with a Change in Dosing (All Doses)	Safety
	X		16.2.5.3	Plasma BCX7353 Pharmacokinetic Concentration Time Data	ITT
X	X		16.2.6.1.1	HAE Attack Diary Detail	ITT
X	X		16.2.6.1.2	HAE Attack Level Summary – Adjusted Attacks	ITT
X	X		16.2.6.1.3	HAE Attack Rate	ITT
X	X		16.2.6.2	Days with Angioedema Symptoms from Adjusted Attacks	ITT
X	X		16.2.6.3	Subject-Level Additional Derived Effectiveness Endpoint Profile	ITT
X		X	16.2.7.1.1	Adverse Events During the SOC Treatment Period	Safety
X		X	16.2.7.1.2	Serious Adverse Events During the SOC Treatment Period	Safety

X	X	X	16.2.7.2.1	Treatment-emergent Adverse Events	Safety
X	X	X	16.2.7.2.2	Serious Treatment-emergent Adverse Events	Safety
X	X	X	16.2.7.2.3	Related Serious Adverse Events	Safety
X	X	X	16.2.7.2.4	Treatment-emergent Adverse Events Related to Study Drug	Safety

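### SAP 6.5.1 makes eligible, enrolled children who withdraw consent during the SOC period screen failures, against the protocol's ITT definition; separately, SOC adverse events in never-dosed children have no assured display

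*SAP*

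**What the plan says.** **Enrollment.** Protocol Section 1 (repeated in 9.2.1): "Subjects will be considered enrolled into the study as of the date of the screening visit", provided the results available by then meet the criteria. Section 9.2.1 adds that the SOC period begins once the child is enrolled.

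**ITT and screen failure in the protocol.** Section 12.2.1.1: ITT "will include all subjects who satisfy all entry criteria and who enroll into the study". The same section counts two groups as screen failures: children with consent who are not enrolled, and preliminary enrollees later found ineligible.

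**Screen failure in the SAP.** Section 6.5.1 starts from consented subjects who qualify thus: "but are not allocated to study treatment, and are noted as screen failures in electronic case report form (eCRF) are considered screen failures". It then adds: "This includes subjects who withdraw consent during the SOC period of the study". On reporting it says: "These subjects will not be treated with study drug and will not be summarized other than on the disposition table". Listing is left open: "Data collected from screen failures may be presented on corresponding data listings".

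**ITT in the SAP.** Section 6.5.2 keeps the protocol's two conditions and adds a third, that the subject is not a screen failure.

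**SOC-period safety displays.** SAP Table 7 assigns tables 14.3.1.15 and 14.3.1.16 and listings 16.2.7.1.1 and 16.2.7.1.2 ("Serious Adverse Events During the SOC Treatment Period") to the Safety population, which requires at least one dose of berotralstat. SAP 11.1 says that every adverse event in the SOC period will be listed. Protocol 4.4.4 gives the SOC period the role of control for the safety assessments.

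**The concern.** A child in the SOC period has already been enrolled. If eligibility is confirmed and the family then withdraws consent, the protocol has an ITT subject who left the study (Section 7.3.1), while the SAP has a screen failure outside ITT. Whoever builds the disposition table must break one of the two documents.

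Two things are at stake. The first is the account of who left before dosing, and why. Eligible children who gave up would be mixed with children who never qualified. The second is the visibility of harm in the period that serves as the safety control. A child with a serious event on SOC who leaves before Day 1 is never dosed, and every planned SOC adverse-event display is restricted to dosed children.

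**Working it through.** No arithmetic decides the conflict; the numbers only show its possible size.

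**1. One child, two labels.** Take a child whose screening results confirm eligibility and whose consent is withdrawn midway through SOC.
- Protocol: enrolled at screening (Section 1, 9.2.1), eligible, therefore ITT (12.2.1.1). Not a screen failure.
- SAP: screen failure (6.5.1), therefore not ITT (6.5.2).

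**2. Effect on disposition.** The planned number is about 30 enrolled. Neither SOC withdrawals nor screen failures are projected. Assume *w* confirmed-eligible consent withdrawals, all flagged as screen failures in the eCRF, and *f* children who truly fail screening.
- ITT falls from 30 to 30 − *w*.
- The screen-failure percentage (SAP 9.1.1) rises from *f*/(30 + *f*) to (*f* + *w*)/(30 + *f*). The increase is *w*/(30 + *f*), at most *w*/30.
- These children leave the discontinuation rows: *w*/30 becomes 0 for this reason for leaving.

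| *w* | ITT, protocol | ITT, SAP | *w*/30 |
|---|---|---|---|
| 1 | 30 | 29 | 3.3% |
| 3 | 30 | 27 | 10% |
| 6 | 30 | 24 | 20% |

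**3. Effect on listings.** Table 7 puts, among others, protocol deviations (16.2.2.2), end of study (16.2.2.3), concomitant medications (16.2.4.4.2) and attack diary detail (16.2.6.1.1) on ITT. A relabelled child leaves all of these, and 6.5.1 makes any listing of the child's data optional.

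**4. SOC adverse-event displays.** The four displays use dosed children. A never-dosed child is outside them whether labelled ITT or screen failure. Correcting 6.5.1 alone therefore changes no number in 14.3.1.15 or 14.3.1.16. This is a second, separate cause.

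Illustration (assumed counts): 3 of 30 withdraw, one with a serious event, and none of the 27 dosed has one. ITT gives 1/30 = 3.3%; Safety gives 0/27 = 0%.

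The direction is open. Assume roughly 40% of dosed children have any SOC adverse event. The all-enrolled rate then depends on how many of the withdrawn children had one, from none to all:

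| Withdrawn | Dosed only | All enrolled, lowest | All enrolled, highest |
|---|---|---|---|
| 1 | 12/29 = 41.4% | 12/30 = 40.0% | 13/30 = 43.3% |
| 3 | 11/27 = 40.7% | 11/30 = 36.7% | 14/30 = 46.7% |
| 6 | 10/24 = 41.7% | 10/30 = 33.3% | 16/30 = 53.3% |

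**5. The plan's own figure.** Protocol 12.1 gives about a 96% chance of seeing at least one treatment-emergent event with a 10% rate in 30 subjects: 1 − 0.9^30 = 0.958, which reproduces. Such events need dosing, and the label does not change who is dosed, so this point leaves that figure alone.

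**The case against.** Several arguments on the other side carry weight.

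- **The relabelling is not what empties the SOC summaries.** A reader might infer that 6.5.1 removes withdrawn children's adverse events and attacks from the SOC control. The documents do not support that. Those tables use the Safety population, and protocol 12.2.1.3 itself assigns safety and effectiveness summaries to dosed children. Using the same children in both periods is also a coherent within-child reference. This stands.
- **SOC attrition does not vanish.** A reader might infer that the CONSORT diagram would show none. The disposition table and diagram cover all subjects, and screen failures appear there with reasons (SAP 9.1.1). The sentence names only consent withdrawal and extends a definition tied to an eCRF flag. Loss to follow-up and investigator discontinuation at Day 1 are not expressly covered. What remains is a wrong label for one group.
- **The control need not look cleaner.** The second table in the working shows that the shift can go either way. This stands.
- **The SAP does promise listings.** Section 11.1 says all SOC events will be listed, and Section 8 says all study data will be. But Table 7 limits the SOC adverse-event listings to Safety, so the SAP contradicts itself and the event's place is not assured.
- **Some SOC withdrawals are proper screen failures.** SAP 6.7.7.3 starts the SOC period at consent, and screening may take 14 days. Consent withdrawn before eligibility is confirmed can fairly be a screen failure. This stands, and is why the sentence should be narrowed rather than deleted.
- **ITT has limited use.** Both documents say so, and in Table 7 it is the named population only for listings. This lowers the severity but does not reconcile the definitions.

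**Conclusion.** Wrong as written, of moderate severity. SAP 6.5.1 and 6.5.2 contradict protocol 12.2.1.1 for confirmed-eligible children who withdraw consent during SOC. ITT and the count of pre-dose discontinuations come out too low and the screen-failure percentage too high, each by the number of such children. Separately, Table 7 conflicts with SAP 11.1, so a serious event on SOC in a never-dosed child has no assured place in a planned adverse-event display.

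The size depends on SOC attrition, which is not stated. The 1, 3 and 6 withdrawals are assumptions, as is the eCRF flag being set for each of them. The effect on SOC incidence has no known size or direction. The primary PK analysis and the treatment-emergent tables concern dosed children and are unaffected, so this is not a point on which the trial's main results turn.

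**What to change.** 1. **Narrow the sentence in SAP 6.5.1.** Screen failures are children not enrolled, found ineligible, or withdrawn before eligibility is confirmed. Confirmed-eligible children who leave during SOC or at Day 1 stay in ITT and appear in the disposition table and CONSORT diagram as *discontinued during SOC, not dosed*, with the reason.
2. **Change the populations in Table 7.** Run listings 16.2.7.1.1 and 16.2.7.1.2 on ITT. Run tables 14.3.1.15 and 14.3.1.16 on ITT alongside the Safety version, which remains the within-child reference. Never-dosed children have no Day 1 cohort, but SAP 11.1 already presents the SOC tables overall.
3. **If SOC attack rates are also shown on ITT,** end the denominator in SAP 6.7.7.3 at the withdrawal date for never-dosed children. The present formula needs a Day 1 date, which they lack.

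The cost is SAP wording, a population flag and a few extra displays. The report will show some SOC-period dropout that would otherwise sit under screen failure.

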6.5.2. Intent to Treat Population

The intent to treat (ITT) population will include all subjects who satisfy all entry criteria, who enroll into the study, and are not considered to be screen failures. As this study focuses on safety and PK of berotralstat, analysis using the ITT population will be limited, with the majority of analyses done using the Safety population.

